4.4. Discontinuation and withdrawal of subjects

The participation in the clinical trial is voluntary and the subjects can decline further participation at any time without providing any motive for the discontinuation. They can also without any given reason at any time demand that their blood and urine samples are destroyed and that their randomization number is removed. If a subject discontinues or is withdrawn from the trial, EoT visit will be performed. In addition, any outcome measures at the ordinary visit that are not covered by the EoT visit will be collected (applicable for visit 4, 6 and 8). AEs will be followed by one (day +7), or if the AEs persists, by two phone calls (day +30).

Withdrawal of subject may take place due to:

- **Incorrect enrolment**

The exclusion criteria (Section 4.2.) apply during the entire study period. Based on the exclusion criteria, subjects will be excluded from the trial before the start of the trial and subjects may also be excluded from the trial and/or study drug during the whole study period

- **Protocol deviations**

The subjects may be withdrawn from the study at the discretion of the investigator if judged non-compliant with study procedures. Subjects will be excluded from the analysis set, if they are no longer judged to fulfill the eligibility criteria; e.g. if the subject has initiated a prohibited medication or other medication not listed or a non-pharmacological treatment considered to compromise the outcome measures in the study. A list of important protocol deviations will be finalized prior to study un-blinding. The number and percentages of

patients with at least one important protocol deviation will be summarized by treatment arm and overall. In addition, the number and percentages of patients within each type of protocol deviation will be provided as well, and a listing of all patients with any important protocol violations/deviations will be provided for the ITT population.

- **Safety Concerns**

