VAR is already tested in subjects with AUD and the interaction with alcohol was found not to be clinical significant (Litten et al., 2013;de Bejczy et al., 2015). In the clinical trials with the combination VAR and BUP, AUD patients have been excluded. However, alcohol-consuming patients were not excluded and alcohol consumption was not an exclusion criteria. No adverse interactions were described (reference studies 1-7 above). Drugs of abuse, including alcohol, enhance DA levels in the brain. Both BUP and VAR increase DA levels in the reward region of the brain. However, BUP and VAR have a slow onset of action and a much lower increase in DA levels and are not judged to have an addictive potential. According to Läkemeldesverket, no reports of addiction to VAR or BUP have been reported (oral communication). The combination of alcohol, VAR and BUP have a theoretical risk of enhancing alcohol's effects and producing a high/false sense of well-being (Volkow and Swanson, 2003), although no such effects were observed in the VAR studies on alcohol. The known increase risks for seizures have been minimized by the exclusion criteria of Epilepsy and alcohol seizures (within 5 years) and need of detoxification. The risk for worsening symptoms of other psychiatric disorders has been minimized by the exclusion criteria. Common side effects of VAR and BUP include e.g. insomnia, dizziness, nausea, all of which are associated with alcohol consumption. These symptoms could possibly be more frequent in the case of VAR, BUP and alcohol in combination.

Risks associated with study specific examinations and sampling

Venous blood will be collected for investigation of eligibility measures and/or outcome measures and/or safety measures at every study visit (9 in total) by professional medical staff (See table 2, section 3.1 for specific investigations). The blood will be drawn from the upper or lower arm. The total amount of blood taken during the whole study will be 245 mL. It is rare for a blood test to result in serious complications but there is a small risk for complications like infections, excessive bleeding, bruising, fainting and dizziness and hematomas. *Action taken to control or minimize above described risks.* Infection control during blood sampling: the medical staff is highly trained and is required to follow the regulations regarding the disposal and storage of needles and blood samples. In rare cases, a wound occurs that become red and swollen, and if

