8.2. Statistical analysis

The main hypotheses that will be tested in a hierachial fashion are:

- Combined treatment with VAR and BUP reduces blood concentrations of B-PEth from baseline and significantly more than double-placebo, VAR or BUP alone.
- VAR reduces B-PEth from baseline and significantly more than double-placebo.

The ANCOVA analysis will compare the mean values of the variable in question for the different treatment groups hierachially. Regulatory agency will consider only one specific primary objective and since the two primary endpoints fulfill regulatory requests independently and separately, no adjustment for multiplicity has been done. As testing between treatments are performed in a hierachial fashion, no adjustment for multiple testing has been done.

The SAS® software, version 9.2 or higher, will be used to produce all of the statistical outputs.

All efficacy and safety variables will be presented using descriptive statistics and graphs as appropriate.

Safety measures will be summarized descriptively using the safety analysis set. Continuous variables will be presented with descriptive statistics (n, mean, standard deviation [SD], median, min, max), within treatment group. Categorical variables will be summarized by treatment group in frequency tables (number of patients and percentage). The denominators for all percentages will be defined as the number of non-missing values for each variable within the analysis set. Percentages will be presented with 1 decimal place.

Primary efficacy variables

- **B-PEth**

One of the primary outcomes will be level of PEth measured in blood.

The primary efficacy variable, B-PEth, is calculated as the mean value over the 8-week steady state active treatment period visit 4 – visit 8 (Day21-Day77) compared to baseline. The data is analyzed as the within patient difference. Day78-Day91 is omitted in the analysis period due to the tendency of drop-out and non-compliance at the end of a study period. Day 0-Day21 is omitted in the analysis due to titration of IMP and optimal timeframe of B-PEth analysis.

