ANCOVA model will have fixed effects for treatment and center and subject, nicotine use and FHP will be entered as random effect.

Definition of analysis sets

Three analysis sets will be used: Modified Intention-To-Treat (mITT), Per Protocol (PP) and Safety. The primary and secondary efficacy endpoints will be estimated using ITT and PP analysis sets separately. The safety endpoints will be analyzed on the safety analysis set.

1) Modified Intention-to-treat (mITT) analysis set

The mITT analysis set will include all trial subjects who complete screening visit and randomization visit and report that they have taken at least one dose of the randomized IMPs. Subjects will be analyzed according to their randomized IMPs.

2) Per-protocol (PP) analysis set

The PP analysis set constitutes all subjects from the ITT population who are considered to be completers. A completer is defined as a subject who:

- has taken the IMP at least 80% of the planned number of days of the active treatment period
- fulfill the visit milestones, where the visit milestones are met by subjects who have:
 - taken part and completed screening visit, Day 0, Day 21, Day 49 and Day 77
 - successful B-PEth analyses at screening visit, Day 0, Day, 21, Day 49 and Day 77
 - completed TLFB data at screening visit, Day 0, Day, 21, Day 49 and Day 77

In case of violation of any of the above-mentioned criteria the subject will not be included in the PP analysis set for the specific outcome variable. Subjects will be analyzed according to their randomized study drug.

3) Safety set

The safety analysis set includes all subjects who report that they have taken at least one dose of randomized study drug, and for whom any post-dose data is available up until Day 77. Patients will be analyzed according to the actual treatment.

Compliance

Adherence to the study drug regimen will be analyzed by pill count and by plasma levels of IMP1 and IMP2 at visit 4 and visit 6.

Randomization issues

Mistakenly randomizing a subject who does not meet the inclusion/exclusion criteria will be considered a protocol violation. Any such subject will not be included in the analysis sets.

Handling of missing data

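### The rule that drops wrongly randomised subjects from the analysis sets contradicts the Safety and mITT definitions, and if applied takes dosed subjects out of the safety tables

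*Protocol*

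**What the plan says.** Section 8.2 of the protocol opens its population definitions with an explicit list: "Three analysis sets will be used: Modified Intention-To-Treat (mITT), Per Protocol (PP) and Safety". The mITT set takes subjects who completed the screening and randomisation visits and report at least one dose, analysed as randomised. For Safety, "The safety analysis set includes all subjects who report that they have taken at least one dose of randomized study drug", provided some post-dose data exist up to Day 77, analysed by the treatment actually taken. Neither definition carries an eligibility condition.

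Under the sub-heading on randomisation issues, the same section says: "Mistakenly randomizing a subject who does not meet the inclusion/exclusion criteria will be considered a protocol violation". The next sentence is the rule at issue: "Any such subject will not be included in the analysis sets".

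The safety output is tied to one population, in two places of Section 8.2: "Safety measures will be summarized descriptively using the safety analysis set" and "The safety endpoints will be analyzed on the safety analysis set".

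Section 4.4 has two related rules. Under protocol deviations: "Subjects will be excluded from the analysis set, if they are no longer judged to fulfill the eligibility criteria". Under safety concerns, a subject also leaves the analysis set when an adverse event is judged to affect the assessments or the trial result. Section 4.4 does not say which set is meant.

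**The concern.** A safety population normally follows exposure: whoever took the drug is counted. Here a second rule, based on eligibility, cuts across that principle and has no exemption for subjects already dosed.

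This matters because the protocol uses eligibility as a safety barrier. Section 7.1 says the criteria are set so that the bupropion contraindications other than AUD itself are avoided, and on seizures: "The known increase risks for seizures have been minimized by the exclusion criteria of Epilepsy and alcohol seizures". A subject who slipped past such a criterion and took the drugs may therefore be one in whom an adverse event is more likely. The event may also be what brings the violation to light, so that the outcome helps to decide who is counted.

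What is at stake is the comparative safety summary of the combination. Section 7.1 states that bupropion has had no controlled trial in alcohol-dependent subjects, and that the earlier trials of the combination excluded AUD patients.

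**Working it through.** The protocol gives no figure to reproduce. The check sets its statements side by side.

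1. **Does the rule reach the Safety set?** It refers to the analysis sets in the plural, after a list of three that includes Safety. Where the authors meant one set they named it: failing a completer criterion removes a subject from the PP set only, for the outcome concerned. The plain reading of the later rule therefore covers all three sets.

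2. **Do the statements conflict?** Take a subject randomised in error who took at least one dose and has post-dose data before Day 77.
   - Safety definition: included, by actual treatment.
   - mITT definition: included, as randomised.
   - Randomisation-issues rule: in neither.

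   These cannot all hold, and Section 8.2 sets no order of precedence.

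3. **What follows if the exclusion is applied?** Safety endpoints and safety summaries use the Safety set alone. The subject leaves the denominator (exposure) and the numerator (events) together. No other section puts the events back into those tables.

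4. **What is not lost?** Section 7.3.1 has all adverse events recorded on the CRF. Section 7.3.3 sends serious adverse events to the sponsor within 24 hours. Section 7.3.5 summarises serious events yearly. Section 4.4 lists important protocol deviations. The loss is confined to the comparative tables.

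5. **Can the event influence the exclusion?** Section 4.4 applies the exclusion criteria throughout the study. Section 9.3 has protocol deviations determined after the end of the study, when the events are known. Section 4.4 finalises the list of important deviations before unblinding, which guards against selecting on arm but not against selecting on events.

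6. **Is it one loose phrase?** No. Both rules in Section 4.4 also remove subjects from an unspecified analysis set after randomisation, and one of them is triggered directly by an adverse event.

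**Scale.** The protocol gives no rate of erroneous randomisation. Assuming 1% to 5%, with all of them dosed:
- overall: 380 × 0.01 = 3.8 to 380 × 0.05 = 19 subjects
- per arm: 95 × 0.01 = 0.95 to 95 × 0.05 = 4.75 subjects

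This counts subjects who might be affected. It does not measure bias, which would also need their event rates by arm.

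**The case against.** The strongest reply is that the outcome is not settled. A reader might infer that wrongly randomised subjects are definitely removed from the Safety set. The documents do not support that, because the Safety definition taken alone keeps them and the protocol refers statistical detail to a SAP that is not at hand. This objection stands, and the point is therefore a contradiction with a harmful reading. It is not an excuse for leaving the text alone: the protocol itself fixes both statements.

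A reader might also infer that the safety conclusion for the combination will be too favourable. That goes too far. The direction is plausible, but events remain in the recording and reporting routes, safety is summarised descriptively with no hypothesis test, and several criteria have nothing to do with risk (the B-PEth threshold, a telephone number, language). Eligibility is also checked at two visits and confirmed in the eCRF before randomisation, so errors may be few.

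A tempting illustration is that losing one seizure would turn 1/190 into zero in the two bupropion arms. The documents do not support using it. Section 7.1 gives about 0.10%, from smoking cessation, hence 190 × 0.001 = 0.19 expected seizures. The seizure would also have to fall in a wrongly randomised subject: at an assumed 1% to 3%, that is 0.19 × 0.01 to 0.19 × 0.03, about 0.002 to 0.006. A higher risk in ineligible subjects would raise this, but the documents do not say by how much.

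Finally, the Day 77 phrase in the Safety definition might be read as cutting off adverse event reporting before dosing ends at Day 91. It is a condition for membership of the set: a dosed subject with any earlier post-dose data qualifies, and the phrase does not say that later events are dropped.

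**Conclusion.** The rule on wrongly randomised subjects is wrong as written. On its plain reading it covers the Safety set, and it contradicts both the Safety and the mITT definitions without any order of precedence. If it is followed, dosed ineligible subjects vanish from the comparative safety tables, with a possible bias towards safety because some criteria guard against harm and an event can expose the violation.

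The size of that bias cannot be derived from the documents. The 4 to 19 subjects above rest on an assumed error rate of 1% to 5% and on all of them having been dosed. The conclusion itself needs neither assumption, since it follows from the text. It does depend on the SAP not having already resolved the conflict; even then the protocol wording would need to agree with it.

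**What to change.** Three text changes, made before unblinding:

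- **Safety set (Section 8.2).** State that every subject who took at least one dose of study drug stays in the Safety set under the treatment received, whether or not eligible.
- **Randomisation issues (Section 8.2).** Restrict the exclusion for ineligibility to the PP set. If the sponsor wants it to reach further, name the efficacy sets concerned and amend the mITT definition to match. PP only is cleaner, because it leaves the mITT definition intact.
- **Section 4.4.** Say which set each of the two exclusions refers to, and that neither applies to the Safety set. The one triggered by an adverse event needs this most.

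The cost is a few sentences in the protocol, with matching wording in the SAP. No new data, visits or subjects are needed.

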9. DATA MANAGEMENT

9.1. Recording of data

An electronic CRFs (eCRF) will be custom-made to the trial by a company appointed by the Sponsor. The trial-specific eCRF will be designed and used to record all the information required by the protocol to be reported on each visit for each trial subject. If, and only if using eCRFs is not possible, a paper CRF may be used. CRFs in paper forms will be available on each site and may be used as source documents if the use of the eCRFs is not possible.

The Investigator will ensure that study specific data are recorded in the eCRF in a timely manner according to instructions eCRF (also the transferal of source data in paper form, if direct incorporation into eCRF is not possible, e.g. laboratory analysis). The Investigator and site personnel will be instructed by the Sponsor in the use of the eCRF. The Investigators must verify that all data entries in the eCRF are accurate. The Investigator and delegated site personell must make all eCRF entries by using a subject-unique login identity. If necessary, the Investigator will be requested to confirm or make corrections, or enter additional or missing data as required bu Queries created in the eCRF. The Investigator will also ensure that any corrections in the CRF, as specified in the study protocol, are in accordance with the instructions provided. The Investigator ensures the accuracy, completeness and timeliness of the data recorded by signing the completed CRF.

The Investigator will have access to all data captured during the trial via the eCRF that is supplied through a secure Internet access. At the end of the trail, the Investigator will also receive a certified copy of all data captures for the study subject.

9.2. Source data and source documents

In accordance with ICH E6, source data is defined as "all information in original records and certified copies of original records or clinical findings, observations, or other activities in the clinical trial necessary for the reconstruction and evaluation of the trial". Source data are contained in source documents (original records or certified copies). Source documents are defined as original documents, data and records. This comprises all hospital records, clinical and office charts connected to the study.

Source documents in the trial comprise:

- eCRF
- Paper copy of CRF in case direct incorporation into eCRF is not possible
- Medical journals and hospital records
- Informed consent form
- Paper laboratory analysis and laboratory notes

- Recorded data from automated instruments, e.g. blood pressure data
- Saliva sticks, e.g. cotinine analysis
- Urine dip sticks with drug identification and pregnancy results
- Study specific spreadsheets and templates
- Study specific regulatory documentation
- SUSAR and SAE documents
- IMP dispensing records and drug accountability records
- Drug accountability and drug dispensing records
- Temperature logs

The Investigator must maintain source documents for each subject in the study. A source data verification log will be included in the Investigator Study File (ISF). The Investigator must ensure that all source documents, i.e. eCRF, progress notes, copies of laboratory and medical test results must be available for inspection and assessment by the Sponsor/coordinating centre, the monitor and/or regulatory authorities.

9.3. Data storage and management

Storage

All data will be recorded, handled and stored in a way that allows accurate reporting, interpretation and verification. After termination of the trial, all source data (paper and electronical files) including ICF, a copy of the completed CRF, original protocol with amendments and the final report will be stored at Sahlgrenska University Hospital, Psychiatry Archive/Addiction Biology Unit, [name] for a minimum period of 15 years in accordance with Swedish regulation/law (Chapter 10, 3 § in LVFS 2011:19).

Data management

Data management will be co-ordinated by the Principal Investigator/ Sponsor. The Sponsor's designated investigational staff will review the data entered into the eCRFs for completeness and accuracy and will instruct the study sites to make any required corrections or additions, by queries issued electronically in the eCRF. Designated site staff is required to respond to the query and confirm or correct the data. Trial data not recorded in the eCRF (e.g. safety and outcome laboratory data) will be transferred to the eCRF system at predefined intervals in a predefined data structure form. Medical history and AE will be coded using the Medical Dictionary for Regulatory Activities (MedDRA). After End-of-Study, the occurrence of any protocol deviations will be determined. After these actions have been completed and the database has been declared complete and accurate, it will be locked and available for data analysis.

Management of laboratory data

Laboratory data will be handled according to the General Data Protection Regulation (EU) 2016/679 (GDPR). The primary outcome variable B-PEth will be analyzed at the Central Laboratory assigned to the Coordinating site. The central lab uses relevant quality systems according to ISO 17024.

The blood samples for B-PEth analysis will be transported to Coordinating site in accordance to Hospital Policy in accordance to required time and temperature conditions. All other analyses, i.e. blood samples for safety measurements and the secondary outcome measures CDT and GGT will be analyzed on site by each site's respective primary blood bank/ by the Investigator appointed local laboratory. Blood samples for analysis of IMP concentrations will be frozen and stored at respective study site. Laboratory data will be incorporated into eCRF by investigational staff only after approval by medical doctor. When all data is

received, alla data problems have been solved and quality control checks have been performed, the study database is considered clean and ready to be locked.

9.4. Study compliance

Study compliance is the adherence to all trial related requirements, to GCP and to regulatory rules and regulations. Non-compliance will lead to prompt action by the Sponsor to secure compliance and may result in closure of the site and notification of the regulatory authorities. Sites with a very low recruitment rate or which persistently violate the protocol may be judged by the Sponsor to stop further recruitment at once or to stop participation in the trial.

10. QUALITY CONTROL AND QUALITY ASSURANCE

10.1. Monitoring

The study will be monitored by independent monitor(s) according to GCP guidelines. The study monitor will be appointed by the Sponsor and will be appropriately trained and informed about the nature of the study, subject written information, GCP and applicable regulatory requirements. The monitor's qualifications will be documented. The monitor should follow the Sponsor's established written SOPs as well as those procedures that are specified by the sponsor in the monitoring plan.

The study will be monitored before, during and after the study period. Before starting the clinical trial, all centers will have a telephone/web-based or physical initiation meeting with presentation of the study, study procedures and documentation. During the study period, monitors will have regular contact with the participating clinics to ensure that the trial is conducted in compliance with the protocol and applicable regulatory requirements. The monitors will also provide information and support to the centers. The number of monitoring visits will be limited, and unless no specific problems occur the main part of the monitoring will be centralized by regular checks of the data quality in the study database. When visiting the clinics, the monitor will review source documents for verification of consistency with the study data recorded in CRF, source data verification. An agreement between the institution and the monitor will be set up to allow the monitor's access to the patient journals. The monitor will submit a written report to the sponsor after each trial-site visit. The monitoring will be further described in the monitoring plan.

